5.2 Trial Treatments

The treatment to be used in this trial is outlined below in [Table 4](#).

Table 4 Trial Treatment

Drug	Dose	Regimen	Route of Administration	Regimen/Treatment Period	Use
ADXS11-001	5 x 10 ⁹ CFU	Q3W	IV infusion	9-week cycle	Experimental

5.2.1 Dose Selection/treatment Modification

The dose to be used in each stage of the trial is described above. Treatment Modification Guidelines are described below in [Section 5.2.1.2](#).

5.2.1.1 Dose Selection

The rationale for selection of doses to be used in this trial is provided in [Section 4.2.2.1](#). The dose of ADXS11-001 will be 5 x 10⁹ CFU, however the sponsor reserves the right to change the dose up to 1 x 10¹⁰ CFU based on emerging data from ongoing clinical studies. If the dose is escalated, subjects who initiated therapy at 5 x 10⁹ CFU may be be escalated up to 1 x 10¹⁰ CFU only after consultation with the sponsor.

The dose of 5×10^9 CFU will not be reduced for individual subject, however, the dose may be reduced for all subjects based on the stopping rules outlined in [Section 4.2.4](#)

Details on the dose calculation, preparation and administration are provided in the Pharmacy Manual.

5.2.1.2 Treatment Modification/Delay Due to Adverse Events

The most likely AEs associated with ADXS11-001 are comprised primarily of individual flu-like symptoms (e.g., fatigue, lethargy and low grade fever) or cytokine release symptoms (e.g., constitutional symptoms such as fever, chills, rigors, headache, nausea, vomiting tachycardia, shortness of breath, hypotension, and rash). These symptoms usually present within 2-4 hours after the completion of infusion and are often mild to moderate and transient in nature or respond quickly to symptomatic treatment. In rare instances they may last up to 24 hours. No cumulative or delayed toxicity has been observed.

Less likely AE's include increase heart rate, low blood pressure, muscle aches, headaches, allergic reaction, changes in blood chemistry, changes in blood counts, and short term changes in liver function.

Rare but serious AEs include high fever, difficulty breathing and hypotension.

██████████ ADXS11-001 has a tropism for the liver. Transient asymptomatic elevations of ALT and alkaline phosphatase were observed after dosing in the Phase 1 trial without prophylactic medication administration. For that reason, patients with significant liver disease are excluded, and particular attention is to be paid to hepatic abnormalities. Treatment may be delayed or discontinued for drug related severe and life-threatening toxicities, as shown below in [Table 5](#).

Table 5 Treatment Delay/Discontinuation Guidelines for Drug-Related Adverse Events

Toxicity	Grade	Hold treatment	Timing for restarting treatment	Discontinue subject
Hematologic	1,2,3	No	N/A	N/A
	4	Yes	Toxicity resolves to \leq Grade 1 or baseline	Toxicity does not resolve to \leq Grade 1 or baseline within 3 weeks
	1	No	N/A	N/A
	2-3	Yes	Toxicity resolves to \leq Grade 1 or baseline	Toxicity not resolved to \leq Grade 1 or baseline within 3 weeks of last infusion ^a

[figure not shown]
Non-hematologic, excluding cytokine release symptoms and DLTs	4	N/A	Permanent discontinuation	Permanent Discontinuation from Study
---	---	-----	---------------------------	--------------------------------------

^a With investigator and sponsor agreement, subjects with a non-heme AE (eg alopecia, neuropathy) still at grade 2 after 3 weeks, may continue treatment if only asymptomatic and controlled

With Investigator and Sponsor agreement, subjects with a laboratory AE still at Grade 2 after 2 weeks may continue treatment in the trial only if asymptomatic and controlled. For information on the supportive care of AEs, see [Section 5.6](#).

Subjects who experience a recurrence of the same severe or life-threatening event at the same grade or greater with re-challenge of ADXS11-001 should be discontinued from trial participation.

5.2.2 Administration of ADXS11-001

5.2.3 Timing of Dose Administration

ADXS11-001 should be initiated on Cycle 1/Day 1 after all procedures/assessments have been completed as detailed on the Schedule of Events ([Section 6.1](#)). Trial treatment may be administered up to 7 days before or after the scheduled treatment day due to administrative reasons but only after consultation with the Sponsor.

All trial treatments will be administered on an outpatient basis.

5.2.4 Pretreatment Prophylaxis Regimen

Mild to moderate cytokine release symptoms (e.g., constitutional symptoms such as fever, chills, rigors, headache, nausea, vomiting, tachycardia, shortness of breath, hypotension, and rash) are commonly seen and typically occur 2-4 hours after ADXS11-001 infusion and often resolve within 12-24 hours. Prophylactic medications are intended to reduce the inflammatory response. Subjects should receive the following pretreatment prophylaxis regimen:

IV Fluid Hydration:

- Normal saline (e.g., 500mL over 30 minutes)

Premedication Regimen:

- Antihistamine- PO or IV (e.g., diphenhydramine 25 mg or equivalent), once
- NSAIDs- PO, (e.g., naproxen, 220 mg or ibuprofen, 400 mg), once
- Antiemetic- PO or IV, (e.g., promethazine or ondansetron), once
- Histamine H₂-receptor antagonist- PO or IV (e.g., famotidine 20 mg or equivalent), once

Pretreatment medication should be given on the day of dosing and completed at least 30 minutes prior to the start of the assigned study treatment. Additional NSAID doses and antiemetic administration should be given per label or package insert post initial administration on Day 1 and Day 2 , as needed. The prescribed dosage of the selected NSAID and antiemetic will be at the discretion of the Investigator.

Do not substitute acetaminophen for the selected NSAID for prophylactic treatment since acetaminophen does not have similar anti-inflammatory properties that could ameliorate cytokine release symptoms.

5.2.5 ADXS11-001 Dosing

The dose for ADXS11-001 will be 5×10^9 CFU administered in 250 mL of normal saline infused over [REDACTED] Q3W in repeating 9-week treatment cycles.

The Pharmacy Manual contains specific instructions for ADXS11-001 storage, handling, dose calculation, reconstitution, destruction and ordering.

All subjects will also receive a 7 day course of oral antibiotics following each ADXS11-001 treatment. Specific details of the antibiotic regimen are provided in [Section 7.1.6.2](#).

5.2.6 Treatment Duration

The study begins when the first subject signs informed consent.

The treatment duration is approximately 2 years.

5.2.7 Trial Blinding/Masking

This is an open-label trial. Therefore, the Sponsor, investigator and subject will know the treatment administered.

5.3 Randomization or Treatment Allocation

All subjects will receive ADXS11-001.

5.4 Stratification

There is no stratification.

5.5 Concomitant Therapies and Procedures (Allowed & Prohibited)

Medications or vaccinations specifically prohibited in the exclusion criteria are not allowed during the ongoing trial. If there is a clinical indication for one of these or other medications or vaccinations specifically prohibited during the trial, discontinuation from ADXS11-001 therapy may be required. The investigator should discuss any questions regarding this with the Sponsor. The final decision on any supportive therapy or vaccination rests with the investigator and/or the subject's primary physician. However, the decision to continue the subject on ADXS11-001 therapy requires the mutual agreement of the Investigator, the Sponsor, and the subject.

5.5.1 Acceptable Concomitant Therapies and Procedures

All treatments that the investigator considers necessary for a subject's welfare may be administered at the discretion of the investigator in keeping with the community standards of medical care. All concomitant medication, therapies and procedures will be recorded on the electronic case report form (eCRF) including all prescription, over-the-counter (OTC), herbal supplements, and IV medications and fluids. Protocol-mandated prophylactic medications and antibiotics should also be captured in the eCRF. If changes occur during the trial period, documentation of drug dosage, frequency, route, and date should be included on the CRF. Only generic names should be used. Do not use trade names.

All concomitant medications received within 28 days before the first dose of trial treatment and up to 30 days after the last dose of trial treatment should be recorded.

5.5.2 Prohibited Concomitant Therapies

Subjects are prohibited from receiving the following therapies during the Screening and Treatment Phase of this trial:

- Anti-cancer therapy including but not limited to, hormonal, chemotherapy, radiation therapy, treatment with targeting agents (eg, Tyrosine kinase inhibitors). However occasional radiation therapy for palliation of pain is allowed
 - Note: Radiation therapy to a symptomatic solitary lesion or to the brain may be allowed after consultation with Sponsor. Radio-pharmaceuticals (e.g., radium, strontium, etc.) are not acceptable.
 - Immunotherapy not specified in this protocol
 - Investigational agents other than ADXS11-001
-

- PI3K inhibitors and TNF α blocking agents
- Live vaccines (eg, measles, mumps, rubella, chicken pox, yellow fever, rabies, BCG, and typhoid) and intranasal influenza vaccines (eg, Flu-Mist®). Seasonal influenza vaccines for injection are generally killed virus vaccines and are allowed.
- Chronic use of systemic glucocorticoids has the potential to reduce the immune response therefore should not be used. However, glucocorticoids should be considered to manage symptoms related to cytokine release. Topical use of steroids is allowed. The intermittent use of steroids for the treatment of COPD and or asthma is allowed.
- Anti-infectives should be avoided. However, subjects with a documented infectious complication should receive oral or IV antibiotics or other anti-infective agents as considered appropriate by the treating investigator for a given infectious condition, according to standard institutional practice.
- Acetaminophen is not to be used for premedication because it does not have anti-inflammatory properties required for AE amelioration but may be used for supportive care measures.

Subjects who, in the assessment by the investigator, require the use of any of the aforementioned treatments for clinical management may be removed from the trial after discussion with the sponsor. Subjects may receive other medications that the investigator deems to be medically necessary.

The Exclusion Criteria ([Section 5.1.2](#)) describe other medications that are prohibited in this trial. There are no prohibited therapies during post-treatment follow-up.

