8. Female subjects of childbearing potential must not be breastfeeding and have a negative urine or serum pregnancy test within 72 hours prior to receiving the first dose of study medication. If the urine test is positive or cannot be confirmed as negative, a serum pregnancy test will be required.
9. Female subjects of childbearing potential should be willing to use 2 methods of birth control for the course of the study through 120 days after the last dose of study medication (see [Section 5.7.2](#)).
10. Male subjects should agree to use an adequate method of contraception starting with the first dose of study therapy through 120 days after the last dose of study therapy.
11. Must have a washout period of the following prior to first dose of study treatment:

- a. **14 days** from completing prior standard of care therapy, with the exception of MMC and palliative radiation therapy for disease-related pain.
- b. **6 weeks** from the last dose of MMC, given the delayed bone marrow suppression that can be experienced with MMC.
- c. **28 days** from treatment with investigational device/therapy or 3 times the half-life in the case of monoclonal antibodies, whichever is longer
- d. **7 days** from treatment with systemic steroid therapy or any other form of immunosuppressive therapy
- e. **30 days** from treatment with live vaccine

Note: Examples of live vaccines include, but are not limited to, the following: measles, mumps, rubella, chicken pox, yellow fever, rabies, BCG, typhoid, and intranasal influenza vaccines (e.g., Flu Mist®). Seasonal influenza vaccines for injection are generally killed virus vaccines and are allowed.

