⁸ All Subjects will receive a 7-day course of oral antibiotic therapy starting approximately 72 hours after administration of ADXS11-001. All subjects will also receive an additional 6 month oral antibiotic course to be initiated approximately 72 hours following the last dose of study treatment or anytime upon discontinuation of study treatment.

⁹ Adverse events and serious adverse events will be assessed from the time Informed Consent is obtained through 30 days after the last ADXS11-001 infusion is administered.

¹⁰ Height will be measured at screening only. Monitor vital signs immediately [REDACTED] for the first 4 hours following the completion of every ADXS11-001 infusion.

¹¹ CID1 Safety labs do not need to be repeated if screening labs are collected within 3 days of dosing. All laboratory procedures are to be completed and assessed by the investigator within 3 days prior to the administration of ADXS11-001 to confirm lab criteria for study treatment are met.

¹² Urine pregnancy tests must be performed within 72 hours prior to each ADXS11-001 infusion for female subjects of childbearing potential. If the urine test is positive or cannot be confirmed as negative, a serum pregnancy test will be required.

¹³ *Lm* Surveillance Monitoring will include a 6-month course of oral antibiotics and routine monitoring of CBC, CMP (including CRP, ESR) and blood cultures. Following completion of the last dose of study treatment or following study discontinuation, all assessments will be performed every 4 months (±2 weeks) for 3 years.

¹⁴ Baseline tumor imaging and assessments must be performed within 28 days prior to the first ADXS11-001 infusion in the first study cycle. Subsequent tumor imaging and assessments will be conducted at Week 8 (±1 week) for the duration of study participation. Radiologic progression, not accompanied by clinical deterioration, should be confirmed ≥4 weeks later.

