7.1.4.8.1 Best Overall Response (RECIST 1.1)

The best overall response is the best response recorded from the start of the study treatment until the end of treatment taking into account any requirement for confirmation. The patient's best overall response assignment will depend on the findings of both target and non-target disease and will also take into consideration the appearance of new lesions (Table 10).

Table 10 Best Overall Response (RECIST 1.1)

Target Lesions	Non-Target Lesions		Overall Response
	Baseline Lesions	Unequivocal New Lesions	
Baseline (Index) and New Measurable Lesions	CR	No	CR

Target Lesions Baseline (Index) and New Measurable Lesions	Non-Target Lesions		Overall Response
	Baseline Lesions	Unequivocal New Lesions	
CR	Non-CR/Non-PD	No	PR
CR	NE	No	PR
PR	Non-PD or NE	No	PR
SD	Non-PD or NE	No	SD
Not all evaluated	Non-PD	No	NE
PD	Any	Yes or No	PD
Any	PD	Yes or No	PD
Any	Any	Yes	PD

CR = complete response; NE = not evaluable at a particular time point; PR = partial response; SD = stable disease; PD = progressive disease

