7.1.4.8.2 Immune-Related Best Overall Response (irRECIST)

The immune-related best overall response (irBOR) is the best irRC overall response over the study as a whole, recorded between the date of first dose until the last tumor assessment prior to subsequent therapy (including tumor resection surgery) for the individual subject in the study (Table 11). As with the primary definitions of tumor response, early progression (i.e., irPD occurring prior to Week 8) will not preclude an irBOR of irCR, irPR or irSD resulting from the Week 8 assessment. An assessment of irPD at or after Week 8 will preclude a subsequent irBOR of irCR, irPR or irSD. However, any post-progression clinical activity in subjects with irBOR of irPD may be summarized for exploratory purposes.

Table 11 Immune-Related Best Overall Response (irBOR)

Target Lesions Baseline (Index) and New Measurable Lesions	Non-Target Lesions ^a		irRC Overall Response
	Total Measurable Tumor Burden	Baseline Lesions	
irCR	irCR	No	irCR
irCR	irSD	No	irPR
irPR	irCR or irSD	No	irPR
irSD	irCR or irSD	No	irSD

Target Lesions Baseline (Index) and New Measurable Lesions	Non-Target Lesions ^a		irRC Overall Response
	Total Measurable Tumor Burden	Baseline Lesions	
irPD	Any	Yes or No	irPD
Any	Unequivocal Progression	Yes or No	irPD
Any	Any	Yes	irPD

irCR = immune-related complete response; irPR = immune-related partial response; irSD = immune-related stable disease; irPD = immune-related progressive disease

^a Any increase in the size or number of non-measurable lesions does not necessarily imply an overall response of irPD. If these lesions become measurable (≥ 10 mm) at a subsequent assessment, their measurement will at that point start to contribute to the total measurable tumor burden. To achieve unequivocal progression of non-target lesions, there must be substantial worsening in non-target disease that is of a magnitude that the Investigator feels it is important to change therapy. Equivocal findings of progression of non-target lesions (e.g., small and uncertain new lesions; cystic changes or necrosis in existing lesions) should be considered irSD, and treatment may continue until the next assessment.

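### No scoring rule covers a target lesion irradiated after the baseline scan, so shrinkage from palliative radiotherapy can be counted as a response to ADXS11-001

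*Combined protocol and SAP*

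**What the plan says.** **Radiotherapy before dose 1.** Inclusion criterion 11a (section 5.1.1) sets a 14-day washout from standard-of-care therapy, "with the exception of MMC and palliative radiation therapy for disease-related pain". MMC then gets its own six-week interval. Palliative radiotherapy gets none.

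**Radiotherapy on study.** Section 5.5.2 applies "during the Screening and Treatment Phase of this trial". It prohibits radiation as anticancer therapy, then states "However occasional radiation therapy for palliation of pain is allowed" and adds a note: "Radiation therapy to a symptomatic solitary lesion or to the brain may be allowed after consultation with Sponsor". Neither sentence is limited to non-target lesions. Subjects who need a prohibited treatment "may be removed from the trial after discussion with the sponsor".

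**Imaging and targets.** Under section 6.1, baseline imaging "must be performed within 28 days prior to the first ADXS11-001 infusion". Section 7.1.4.3 fixes the target lesions at baseline (at most 2 per organ and 5 in total). Section 7.1.4.2 classes lesions in a previously irradiated area as non-measurable unless they are new since that radiotherapy.

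**Scoring.** Section 7.1.4.4 defines CR by disappearance of the targets and PR by a fall of at least 30% in their sum from baseline. Section 7.1.4.8.1 gives the RECIST 1.1 window: "The best overall response is the best response recorded from the start of the study treatment until the end of treatment". For irRECIST, section 7.1.4.8.2 ends the window differently: "until the last tumor assessment prior to subsequent therapy (including tumor resection surgery"). Section 8.3.1 defines PFS and its censoring without mentioning local therapy.

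**The concern.** Response by RECIST 1.1 is a primary endpoint, and there is no control arm against which shrinkage caused by radiotherapy would cancel out. A painful lesion that is irradiated may shrink because of the radiation. If that lesion is a target, the plan's rules credit the shrinkage to ADXS11-001. The trial is open label, and central review appears only in Appendix 12.3, for exploratory volumetric analysis.

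The Stage 1 response gate is only a few subjects wide, so a single misattributed response can matter. For PFS, radiotherapy to a growing target can postpone radiologic progression past six months. That direction is less certain, because section 7.1.4.4 measures progression from the smallest sum on study, and a sum lowered by radiotherapy also lowers that reference.

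**Working it through.** The plan prints no figure on this point. Its operating characteristics (section 8.2) say nothing about misattributed responses. The printed expected sample size does reproduce: 31 + 24 × (1 − 0.94992) = 32.20192. The printed type I error and power cannot be checked, because the simulated cell probabilities and final cut-offs are not given. Neither result bears on this point.

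**Step 1: which lesions are exposed?**

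| When the lesion is irradiated | Rule that applies | Can its shrinkage count? |
|---|---|---|
| Before the baseline scan | 7.1.4.2: non-measurable | No, it cannot be a target |
| After the baseline scan, before dose 1 (a gap of up to 28 days) | None | Yes |
| On treatment, between scans | None | Yes, until treatment ends |

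**Step 2: can one irradiated lesion produce a PR?** Take k target lesions of equal size, with the others unchanged, no new lesions and no non-target progression. The irradiated lesion must shrink by 0.30 × k for the sum to fall 30%:

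- k = 1: 30%
- k = 2: 60%
- k = 3: 90%
- k = 4 or 5: 120% or 150%, which is impossible from one lesion alone

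One measurable lesion is enough for measurable disease (7.1.4.2), so the symptomatic solitary lesion of section 5.5.2 can be the whole target sum.

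**Step 3: effect on the observed rate.** One subject is 1/31 = 3.2 points in Stage 1 and 1/55 = 1.8 points overall. Section 8.2 gives two readings of the Stage 1 response gate:

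- Three or more responses: 2/31 = 6.5% becomes 3/31 = 9.7%.
- A rate of at least 10%: 3/31 = 9.7% becomes 4/31 = 12.9%.

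One subject can cross either gate.

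**Step 4: chance of passing the response gate.** The true response rate p and the number m of misattributed responders are assumptions; the documents give neither. With gate g, the chance is P(X ≥ g − m), where X is binomial with 31 − m subjects and rate p.

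| True rate p | Gate | m = 0 | m = 1 | m = 2 |
|---|---|---|---|---|
| 3% | 4 of 31 | 1.3% | 6.0% | 21.6% |
| 5% | 4 of 31 | 6.7% | 18.8% | 42.9% |
| 8% | 4 of 31 | 23.3% | 43.5% | 68.6% |
| 5% | 3 of 31 | 20.1% | 44.7% | 77.4% |

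**Step 5: the other gate.** Stage 2 also opens on a 6-month PFS rate of at least 20%. Treated as a simple proportion, 0.20 × 31 = 6.2, so 7 of 31. At true PFS rates of 10%, 15% and 20% this gate is met with probability 3.1%, 17.3% and 42.9%, and an extra responder then changes nothing. For p = 5%, gate 4 of 31 and m = 1, the gain is 18.8 − 6.7 = 12.1 points. If the two endpoints were independent (a rough assumption), the gain in the chance of opening Stage 2 would be:

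- 12.1 × 0.969 = 11.7 points
- 12.1 × 0.827 = 10.0 points
- 12.1 × 0.571 = 6.9 points

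**The case against.** **Controls exist.** Radiotherapy is prohibited as a rule; the allowance is occasional and for pain, and treating a solitary lesion requires sponsor consultation. Section 5.5 requires mutual agreement to continue a subject who needs a prohibited therapy, section 5.5.2 allows removal (which would end treatment and close the RECIST 1.1 window), and section 5.8 lists clinical progression as a reason to stop. A reader might therefore go too far in inferring that nothing limits the problem. These controls do reduce exposure. But they are discretionary, and none says how a lesion is scored when the subject stays on treatment.

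**Resection.** A reader might infer that a resected target may also be scored as a response. The documents do not support this: no section permits resection of a target lesion, and section 5.7.5 deals with surgery in general. At most, a scoring rule is missing if such a procedure happens.

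**The irRECIST contrast.** A reader might infer that the secondary criterion is protected and the primary one is not. That is not established. The irRECIST window covers the whole study and so needs a cut-off at later therapy, while the RECIST 1.1 window already closes when treatment ends. The irRECIST text names resection but not radiotherapy, and palliative radiotherapy during treatment is not clearly subsequent therapy. The gap affects both criteria.

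**Frequency.** An irradiated subject is not automatically a false responder, as Step 2 shows. This stands, and the probabilities above are illustrations.

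**Deferral to a SAP.** Section 8.1 leaves analysis detail to a SAP, and no separate SAP text is supplied. That tempers the remark on PFS censoring. It does not answer the response point, because the protocol itself states the response rules.

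**Conclusion.** The concern holds in a limited form. For a target lesion irradiated after the baseline scan, the response rules as written credit the shrinkage to the study drug. That is a stated rule giving a wrong answer for a primary endpoint, and the error favors the drug.

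The firm size is 3.2 points per misattributed responder in Stage 1, enough to cross the response gate under either reading of section 8.2. It would be too strong to say that 3 of 31 fails: the 10% rule says so, but the same section opens Stage 2 at three responses. The Stage 1 decision changes only when the 6-month PFS gate is not met. The gate probabilities rest on assumed true rates and an assumed one or two misattributed subjects.

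The effect on PFS is possible but less certain in direction. The documents do not support treating every irradiated subject as a PFS failure, since that would penalize pain relief for a stable non-target lesion.

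**What to change.** 1. **Best response.** In sections 7.1.4.8.1 and 7.1.4.8.2, naming radiotherapy explicitly in both, state that best response uses only assessments made before radiotherapy to, or any local procedure on, a target lesion. A CR or PR first seen afterward does not count.
2. **Radiotherapy between the baseline scan and dose 1.** State that such a subject stays in the denominator and cannot be counted as a responder on that lesion. Saying so matters because section 5.9 replaces non-evaluable subjects; scoring these subjects as non-evaluable would remove them from the rate.
3. **PFS.** Leave the primary definition unchanged. Add two sensitivity analyses of the 6-month rate for subjects whose target lesion was irradiated before the landmark: one censoring them at the last prior scan, the other counting them as not progression-free.

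**Cost.** The change is wording plus one data item. Section 5.5.1 already has therapies and procedures recorded on the eCRF but does not say that the irradiated site is captured; it must be, and linked to the target lesions. The reported response rate may fall slightly. Which palliative treatments are permitted does not change.
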